## Participant retention

Even with the \$20 per survey completion incentive, we expect a certain amount of drop off in survey participation. Our primary outcome is vaccination status. Thus, mothers who do not participate in all the study surveys are eligible for primary study outcome assessment, so long as their child maintains coverage and continues to seek care within the KPCO health system. Our previous studies indicate the proportion of children who discontinue KPCO coverage after the birth to be ~15%, and our study is powered with this attrition in mind.

# **Analysis**

Total days undervaccinated will be analyzed in two ways. First it will be done using a dichotomous variable (up-to-date vaccination status). Second analysis will be done as a continuous measure. The dichotomous variable will be analyzed using logistic regression to estimate odds ratios and associated 95% confidence intervals. We will use a nonparametric analysis and a rank transformation approach to assess the continuous measure as total days undervaccinated has a highly skewed distribution. We will use a modified intention to treat framework. To ensure vaccination data available for assessment of outcomes, this analytic cohort will include infants of all randomized mothers who maintained KPCO health coverage for the allotted amount of time (200 days for the primary outcome, 489 days for the secondary outcome) with no more than 90 days of no coverage. For both vaccination behavior measures, if a statistically significant association is observed in the primary analysis, we will conduct analyses stratified by baseline vaccine hesitancy as measured by the 5-item vaccine hesitancy scale described above (Olejado).

For survey measures, we will assess changes in vaccine attitudes and intention over time. All survey items are measured using Likert scales and will be analyzed as linear measures. For each survey outcome average change over time by arm will be assessed using a repeated measures ANOVA. Mixed linear models will be used to assess the "difference in difference" over time in these means, by arm, controlling for the covariates. To ensure survey outcomes for analysis, we will use a modified intention to treat analysis that includes all participants with data from at least one non-baseline questionnaire.

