#### Randomization

Participants are randomized using stratified randomization along with permuted block technique using a 1:1:1 allocation ratio between the VAYB, untailored and usual care arms. Randomization occurs using software embedded in the study website immediately following enrollment into the study. Randomization remains in place throughout the study. Participants are first stratified into either a hesitant or non-hesitant group, based on vaccine hesitancy status from the baseline questionnaire. Hesitancy status is assessed using a 5-item validated measure developed by Opel DJ (olejado). Participants are categorized based on the measure's suggested (but unpublished) cutoffs. Participants from each group are then added to their own set of blocks that each contain 6 slots. There are 2 slots available for each of the 3 study arms. These slots are randomly ordered when the block is created. When all 6 slots are filled, a new block with 6 randomly ordered slots is added.

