# 2. Vaccination attitudes and hesitancy

Vaccine attitudes and hesitancy was in a questionnaire online. These data are used to assess changes over time in vaccination attitudes and hesitancy, and how these relate to study arm, vaccination values, and vaccination status. Vaccination attitudes are assessed using measures previously developed by our team and others. vaccine values are assessed using a novel framework we have developed, and vaccine hesitancy is assessed using a 5-item validated measure (Olejado). A variety of covariates and potential moderators will be assessed as part of this analysis including parent age, gender and insurance coverage type (such as Medicaid and HMO), and mother's age, race, and ethnicity. Also included will be metrics measuring website engagement (VAYB and Untailored arms only) including time spent on the website, number of times viewing website, number and order of pages viewed, and match between stated concerns and website material viewed (VAYB arm only).

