# Missing data

Nearly all vaccines provided to KPCO patients are documented in the EMR, and doses provided outside KPCO are documented in Colorado Immunization Information System (CIIS). Therefore, we expect minimal missing data for vaccination outcomes. To ensure the most complete record, CIIS will be cross checked for all participants to identify any vaccine doses given to infants outside the KPCO system that are missing from the KPCO EMR. Participants who do not have vaccination data present in either system will be assumed to have not gotten a vaccine dose elsewhere.

For survey data, due to our recruitment strategy, we anticipate no missing data at baseline, as completion of the baseline survey was a criterion study enrollment. However, there may be missing data for subsequent surveys as completion of the subsequent surveys was not required to remain in the study. For missing data in surveys beyond baseline, multiple imputation models will be developed for analyses involving multiple survey points where greater than 10% of subjects would be lost due to missing values.

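### The logistic and rank analyses of vaccination name no term for the hesitancy stratum used in randomisation; the tests stay valid but may lose some power

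*Combined protocol and SAP*

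**What the plan says.** The Randomization section uses 1:1:1 permuted blocks of six, kept separately for two groups: "Participants are first stratified into either a hesitant or non-hesitant group, based on vaccine hesitancy status from the baseline questionnaire".

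For up-to-date status at 200 days, the Analysis section says: "The dichotomous variable will be analyzed using logistic regression to estimate odds ratios and associated 95% confidence intervals". For total days undervaccinated it says: "We will use a nonparametric analysis and a rank transformation approach to assess the continuous measure". Neither sentence names a covariate or a stratum term. The one mention of adjustment, "by arm, controlling for the covariates", belongs to the mixed linear models for the survey outcomes.

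For both vaccination measures, if the primary analysis is significant, "we will conduct analyses stratified by baseline vaccine hesitancy". The text refers there to the 5-item scale and not expressly to the two-level category used for allocation. No estimate comparing the effect between the two hesitancy groups is mentioned.

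On completeness of the stratum variable, the Missing data section says: "we anticipate no missing data at baseline, as completion of the baseline survey was a criterion study enrollment".

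**The concern.** Stratified blocking makes the arms nearly equal in their share of hesitant mothers. If hesitancy predicts vaccination, this removes a source of chance difference between arms. An analysis that leaves the stratum out still counts that source in its standard error, so the standard error is too large for the design. The test then rejects less often than its nominal 5% under the null and has less power than the design allows. At stake is some efficiency in the primary comparison, for want of one variable already held for every participant.

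The second, smaller matter is presentation. Stratum-specific results shown side by side invite a comparison of significance. The smaller stratum has less information, so one stratum will often be significant and the other not even when the effect is the same in both.

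**Working it through.** The documents give no figure to reproduce: no arm size, up-to-date rate, hesitant share or effect size. The only usable input is the expected loss of coverage of about 15% (Participant retention). Everything else below is assumed. All calculations are for one two-arm comparison.

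**Assumed cases** (hesitant share h; up-to-date rate in non-hesitant p_n / hesitant p_h): A 15%, 92%/60%; B 20%, 92%/55%; C 10%, 90%/75%; D 15%, 80%/65%.

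**Step 1, direction and size under the null.** Let r be the within-stratum variance divided by the marginal variance of the binary outcome:

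r = [(1−h)p_n(1−p_n) + h p_h(1−p_h)] / [p(1−p)], with p = (1−h)p_n + h p_h.

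With exact stratum balance, the actual two-sided level of the unadjusted test is 2[1 − Φ(1.96/√r)]. Random 15% loss restores 15% of the between-stratum variance, so r becomes r′ = r + 0.15(1 − r).

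Case A: p = 0.85×0.92 + 0.15×0.60 = 0.872. Marginal variance = 0.872×0.128 = 0.1116. Within-stratum variance = 0.85×0.0736 + 0.15×0.24 = 0.0986. So r = 0.883, r′ = 0.901, and the level is 2[1 − Φ(1.96/√0.901)] = 3.9%.

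The same steps for B, C and D give r = 0.832, 0.980 and 0.983, and levels of 3.4%, 4.8% and 4.8%.

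**Step 2, simulation of the logistic analysis.** 200,000 comparisons per case; 471 randomised per arm with equal stratum sizes by arm; each child kept with probability 0.85 (about 400 analysed per arm); Wald tests with and without the stratum; conditional odds ratio 1.8 for power.

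| Case | Null rejection, without / with stratum | Power, without / with stratum | Gain (points) |
|---|---|---|---|
| A | 3.8% / 5.0% | 61.5% / 65.9% | 4.4 |
| B | 3.4% / 4.9% | 65.1% / 71.3% | 6.2 |
| C | 4.8% / 5.0% | 63.6% / 64.4% | 0.8 |
| D | 4.9% / 5.1% | 87.8% / 88.1% | 0.3 |

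The null column agrees with step 1. The gain shrinks in large arms: 0.7–6.4 points at 200 analysed per arm, 0.3–6.2 at 400, 0.1–3.2 at 700 and 0.0–1.2 at 1000.

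**Step 3, the rank analysis.** 20,000 simulations per case with the same loss. Days undervaccinated were assumed zero-inflated exponential (mean 40 if late and non-hesitant, 150 if late and hesitant, capped at 648). Null rejection without the stratum in A–D was 3.8%, 3.3%, 4.8% and 4.7%. Power without the stratum was 61.6%, 65.1%, 64.1% and 87.7%. With the stratum as a covariate on ranks it was 66.1%, 71.5%, 64.9% and 88.2%; with a van Elteren test, 65.3%, 70.0%, 64.7% and 88.0%.

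**Step 4, what adjustment does to the estimate.** In case A the mean log odds ratio moves from 0.534 (odds ratio e^0.534 = 1.71) to 0.597 (1.82), and its standard error from 0.238 to 0.253. The standard error rises, but the ratio of estimate to standard error rises too: 0.534/0.238 = 2.24 against 0.597/0.253 = 2.36.

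**Step 5, the stratified up-to-date results.** With the same conditional odds ratio of 1.8 in both strata and a significant overall pairwise test, exactly one stratum is significant in 63%, 61%, 74% and 67% of trials at 400 per arm. The range over cases is 64–73% at 200 and 31–62% at 1000. An interaction test rejects in 4.3–5.0% of the same trials at 400. The standard error of the log ratio of odds ratios at 400 is 0.511, 0.471, 0.636 and 0.462, so its 95% CI extends by a factor of e^(1.96×SE) = 2.72, 2.52, 3.48 and 2.47 either side.

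**The case against.** **Silence is not a decision to omit.** The Analysis section names a model family and an effect measure; it does not say that the models are unadjusted. Both methods can carry the stratum. This stands: the plan leaves the term unspecified, and the loss arises only if the analysis is run as written.

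**The gain may be trivial.** Two of the four cases gain less than one point at 400 per arm. The larger gains assume differences of 32 and 37 percentage points between strata, and the Randomization section says that the hesitancy cutoffs are unpublished. This also stands, and limits the point to a low-cost efficiency gain.

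**The interaction can be derived.** If the stratum odds ratios are reported with 95% CIs, a reader can subtract the log odds ratios and add the squared standard errors. That is correct. What is missing is a line of presentation, and the plan nowhere says that it will compare significance across strata. The frequencies in step 5 measure the risk of a misreading, not a planned inference.

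**Stronger readings that the documents do not support.** A reader might infer that ignoring the stratum inflates false positives or invalidates the primary test; the effect runs the other way. A reader might fault the secondary outcome on attitudes and hesitancy, which covers "how these relate to study arm, vaccination values, and vaccination status", for containing no vaccination model. That section concerns attitude and hesitancy outcomes and is not part of the defect. A reader might also object to running the stratified analyses only after a significant primary result; that condition is a recognised guard and is not criticised here.

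**Conclusion.** The point holds as one of efficiency and specification. Randomisation is stratified by hesitancy, and the two vaccination analyses name no term for it. Run as written, with hesitancy prognostic, they are valid but conservative. At 400 analysed per arm the logistic power loss is about 0.3 to 6 points under the assumed cases, and the rank analysis behaves similarly. With a weakly prognostic stratum or large arms the loss is negligible. The true size for this trial cannot be determined from the documents, because the hesitant share, up-to-date rates, arm size and effect size behind these figures are all assumptions.

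The stratified-results part is secondary and concerns reporting only.

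**What to change.** In the Analysis section:

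- State that the two-level hesitancy stratum, as randomised, is a term in the primary logistic model. Saying *as randomised* also settles whether the category or the 5-item score is meant.
- State that the rank analysis of days undervaccinated is adjusted for the same stratum or stratified by it, for example with a van Elteren test.
- Where the hesitancy-stratified up-to-date analyses are run, report beside the stratum odds ratios the ratio of odds ratios with its 95% CI for each planned pairwise arm comparison. Label it exploratory and expected to be imprecise. No interaction estimate is asked for in the rank analysis, where no readily interpretable scale is at hand.

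The cost is a few sentences, one model term, and one table row per pairwise comparison: two rows if the tailored arm is compared with each of the other arms, three if all pairs are compared. No new data are needed, since the stratum must be known before a participant can be allocated. The downside is that the primary odds ratio becomes conditional on stratum and so is not the same quantity as an unadjusted one; the report should say so. At 400 per arm, the ratio of odds ratios could not rule out moderate differences between strata.

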#### Consent and Recruitment

Eligible participants are sent a series of 2 letters, 3 emails, and one phone call 1-2 weeks apart. Participants are directed to the KPCO study registration website created specifically for this study. On this registration website the participants identity and eligibility are confirmed, and consent is electronically signed.

After consent, participants are directed to the *study* website where they set up login information and are provided with a Baseline Questionnaire.

The following topic areas are assessed in the Baseline Questionnaire:

- 1. intention to vaccinate
- 2. vaccination values
- 3. logistical barriers to vaccination

- 4. vaccine attitudes and beliefs (vaccination concerns)
- 5. vaccine hesitancy (used for randomization)
- 6. demographics.

Upon completion of this questionnaire, participants are considered to be "enrolled" in the study and are randomized.

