#### **Outcomes**

Primary: Vaccination status

Vaccination data is collected routinely as part of clinical care within the KPCO health system and will be assessed from the KPCO EMR at pre-defined ages (200 days and 489 days). Colorado Immunization Information System (CIIS) will be used as a secondary vaccination data source, though internal audits demonstrate that >95% of childhood vaccines given to KPCO patients are captured within the EMR.

The primary outcome of the study is a dichotomous categorization of vaccination status (up-to-date vs. not up-to-date) that is defined based on a continuous measure of days under-vaccinated. This outcome is assessed at 200 days of age to cover vaccines in the initial infant vaccination series and to minimize the loss to follow-up. The following 6 vaccines recommended by the Advisory Committee on Immunization Practices will be assessed: hepatitis B; rotavirus; diphtheria-tetanus-acellular pertussis; Haemophilus influenzae type b; pneumococcal conjugate vaccine; and polio.

To categorize vaccination status, we will first assess the number of days under-vaccinated for the 2- and 4-month vaccines (combined), by calculating the difference between when a vaccine dose was actually administered and when a vaccine dose should have been administered according to the vaccination schedule recommended by the Advisory Committee on Immunization Practices,² plus an additional 30 day "leeway" to account for vaccination that did not occur at exactly the minimal interval between doses. For example, the first dose of rotavirus vaccine is due at age 2 months (61 days) but is not considered late until age 92 days. Days undervaccinated for this dose begin accruing on day 93. The number of days under-vaccinated is then summed across all doses and vaccines to calculate a total number of days undervaccinated for each infant and can range from 0-648 days. Infants with 0 total days undervaccinated (assessed specifically for the 2 and 4 months vaccines) at 200 days will be considered up-to-date on their vaccination status; those with ≥1 days undervaccinated will be considered not up-to-date.

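### No covariates are named for the vaccination analyses, although baseline intention and the hesitancy stratum are known for every mother before randomisation; leaving them out would be valid but may cost power.

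*Combined protocol and SAP*

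**What the plan says.** The Outcomes section defines the primary endpoint: "The primary outcome of the study is a dichotomous categorization of vaccination status (up-to-date vs. not up-to-date"), assessed at 200 days of age. The Analysis section gives its method in one sentence: "The dichotomous variable will be analyzed using logistic regression to estimate odds ratios and associated 95% confidence intervals". For total days under-vaccinated on the continuous scale it says: "We will use a nonparametric analysis and a rank transformation approach to assess the continuous measure". Neither sentence lists a covariate.

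Baseline hesitancy appears in the vaccination analyses only as a subgroup variable, to be used if the primary result is significant. Control for covariates is stated only for the mixed models of the survey outcomes. The covariates listed under Secondary Outcomes belong to the attitudes and hesitancy analysis and do not include baseline intention.

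Two relevant variables exist before allocation:

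- Under Consent and Recruitment, the first Baseline Questionnaire topic is "intention to vaccinate". It is listed separately from the hesitancy measure, and mothers are randomised only after completing the questionnaire. The Missing data section adds: "we anticipate no missing data at baseline, as completion of the baseline survey was a criterion study enrollment".
- Under Randomization: "Participants are first stratified into either a hesitant or non-hesitant group, based on vaccine hesitancy status from the baseline questionnaire".

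**The concern.** A baseline variable that predicts whether an infant is vaccinated on time can sharpen the comparison between arms if it is in the model. Intention is a plausible candidate. It is the mother's own plan about the behaviour that the endpoint measures, it is among the variables used to tailor the website, and it is graded, so it can carry information within each level of a two-level stratum. The hesitancy group is the more basic candidate, because randomisation was stratified on it.

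What is at stake is power for the tailored arm against the untailored arm and against usual care, and precision in the rank analysis. There is also a question of prespecification: while the covariates are unstated, an adjusted and an unadjusted result could each be presented as the planned one.

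**Working it through.** **Inputs from the documents.** Binary primary endpoint; logistic regression; three arms "using a 1:1:1 allocation ratio between the VAYB, untailored and usual care arms"; about 15% loss of coverage (Participant retention); "odds ratios and associated 95% confidence intervals", from which a two-sided 5% level is inferred. The documents give no sample size, target power, effect size or up-to-date rate, so there is no figure of the plan's own to reproduce.

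**Assumptions, none from the documents.** One pairwise comparison; three pairs of up-to-date rates; 15% of mothers hesitant; a five-point intention item with 65% in the top category; latent correlation 0.5 in size between hesitancy and intention (more hesitant, lower intention); odds ratio 2 for hesitancy; odds ratio per SD of intention from 1.0 to 3.0; simple randomisation.

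**Step 1: arm size.** For 80% power without covariates,

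n = [1.96·√(2p̄(1−p̄)) + 0.842·√(p₁(1−p₁)+p₂(1−p₂))]² / (p₂−p₁)².

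- 70% v 80%: (1.200 + 0.512)²/0.01 gives 294 per arm; 294/0.85 gives 346 enrolled.
- 80% v 88%: (1.016 + 0.434)²/0.0064 gives 329; 329/0.85 gives 388.
- 85% v 92%: (0.884 + 0.377)²/0.0049 gives 325; 325/0.85 gives 383.

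**Step 2: simulated power.** There were 2,000 trials per scenario, with every model fitted to the same data and a Wald test of arm. Entries are power (%) with no covariate / stratum only / stratum plus intention. The bracket is the gain, in points, from adding intention to the stratum model.

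| OR per SD of intention | 70% v 80% | 80% v 88% | 85% v 92% |
|---|---|---|---|
| 1.0 | 80.8 / 80.7 / 80.4 (−0.3) | 82.4 / 82.6 / 82.7 (+0.1) | 83.2 / 83.2 / 82.9 (−0.3) |
| 1.3 | 80.0 / 80.6 / 81.4 (+0.8) | 79.4 / 80.0 / 80.4 (+0.4) | 80.2 / 79.6 / 80.4 (+0.8) |
| 1.6 | 79.6 / 80.8 / 82.0 (+1.2) | 80.6 / 82.1 / 83.5 (+1.4) | 82.0 / 82.2 / 83.5 (+1.3) |
| 2.0 | 78.7 / 80.4 / 84.1 (+3.7) | 81.2 / 83.3 / 87.6 (+4.3) | 81.0 / 82.0 / 86.0 (+4.0) |
| 3.0 | 80.9 / 82.0 / 90.6 (+8.6) | 81.0 / 83.5 / 91.8 (+8.3) | 78.0 / 81.2 / 89.6 (+8.4) |

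A single power figure has a simulation standard error of about √(0.8×0.2/2000) = 0.9 points. Comparisons within a row of models are tighter, because the models share data sets. Moving from no covariate to both gains 5.0 to 6.4 points at an odds ratio of 2.0 (84.1−78.7, 87.6−81.2, 86.0−81.0). With no intention effect, adding it changes power by at most 0.4 points in any of these comparisons, with or without the stratum.

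**Step 3: the rank analysis.** If r is the partial correlation of intention with ranked days, given the stratum, the equivalent gain in sample size is 1/(1−r²) − 1. For r = 0.18 this is 3%; for 0.25, 7%; for 0.3, 10%; for 0.4, 19%. With 84% of infants up to date and tied at zero, 15% hesitant, days late among late infants unrelated to intention, and 0.5 log-odds per SD (odds ratio 1.65), r comes to about 0.18 to 0.25 across three assumed intention distributions. The weak-to-moderate case is therefore worth roughly 3 to 7% more infants; 10% or more needs a stronger predictor.

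**The case against.** The strongest reply has four parts.

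- **Silence is not exclusion.** A reader might infer that the plan commits to an unadjusted test and so discards power. The text does not support that: it leaves the model's covariates unstated. This stands, and the point is worded accordingly.
- **The prognostic strength is unknown.** Nothing in the documents shows that intention is the best baseline predictor. The endpoint is strict: one late day on any 2- or 4-month dose makes an infant not up to date, so a mother who fully intends to vaccinate can miss it for practical reasons. The questionnaire also covers logistical barriers and vaccine concerns. The documents give no number of items, scoring or distribution for intention. This also stands, and it is why the gain is given as a range that starts at zero.
- **Large gains need a very strong predictor.** With independent strata and intention, a separate simulation reached about 10 points, but only at 1.5 log-odds per SD within stratum, an odds ratio of about 4.5. That should not be offered as the expected gain.
- **The trial may be adequately powered anyway.** Participant retention says that the study is powered with attrition in mind. A reader might infer that it is underpowered or biased without adjustment; nothing in the documents shows either.

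None of this argues against naming the covariates. The data are already collected, and the simulated cost of including a useless one is negligible.

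**Conclusion.** The point holds as an avoidable gap in specification with a possible loss of efficiency. It is not a flaw in validity. The covariates of the vaccination models are unstated, and two complete pre-randomisation variables are available for them.

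The size cannot be fixed from the documents. Beyond the stratum, intention adds 0.4 to 1.4 points of power at an odds ratio of 1.3 to 1.6 per SD, 3.7 to 4.3 points at 2.0 and 8.3 to 8.6 points at 3.0. These figures rest on the assumed rates, hesitancy prevalence, item distribution and correlation listed above. The direction is secure if intention is prognostic; the amount is not.

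**What to change.** In the Analysis section, before unblinding, state that the logistic models for up-to-date status (200 and 489 days) and a linear model on ranked days under-vaccinated include both:

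1. the two-level hesitancy stratum used in randomisation; and
2. the intention score from the Baseline Questionnaire, with its scoring given.

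State that only this pre-randomisation reading may be used. The All arms section describes a further intention reading, collected by e-mail after exposure to the intervention; that one must never enter as a covariate, and neither may later survey readings. State whether the target odds ratio is conditional or marginal and, if marginal, that it is obtained by standardisation. Keep the model without intention as a supporting analysis.

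The cost is a few sentences. No new data are needed, and no infants should be lost, because the baseline questionnaire is expected to be complete. The one real drawback is that the adjusted odds ratio is conditional on the covariates unless it is standardised, so it would not be directly comparable with an unadjusted one.

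### Survey outcomes are compared by change from baseline, and the plan names neither the baseline score as a covariate nor a common baseline mean; on the ordinary reading this costs precision but adds no bias

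*Combined protocol and SAP*

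**What the plan says.** The Analysis section describes two analyses of the survey measures. The first is change within arm: "For each survey outcome average change over time by arm will be assessed using a repeated measures ANOVA". The second is a mixed linear model for the difference-in-difference "over time in these means, by arm, controlling for the covariates". No model equation is given.

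The covariates are described under Secondary Outcomes, item 2: "A variety of covariates and potential moderators will be assessed as part of this analysis including parent age, gender and insurance coverage type", followed by the mother's age, race and ethnicity and by website engagement measures. The list is open. It does not name the baseline score of the outcome or the hesitancy stratum used in Randomization. Neither section says that the arms are given a common baseline mean.

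On scale, the plan says: "All survey items are measured using Likert scales and will be analyzed as linear measures". On baseline completeness, the Missing data section says: "we anticipate no missing data at baseline, as completion of the baseline survey was a criterion study enrollment".

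**The concern.** In a longitudinal mixed model, difference-in-difference ordinarily means the arm-by-time contrast with a separate baseline mean for each arm. Each arm's observed baseline mean is then subtracted in full. In a randomized trial the expected baseline means are equal, so full subtraction brings in chance baseline differences. Regression on the baseline score removes only the part of baseline that predicts follow-up, which leaves a smaller variance.

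The comparisons at stake are the secondary aim (attitudes), intention, and hesitancy. Hesitancy is listed as a secondary outcome but also appears in the primary hypothesis under Aim and Hypothesis. If the ordinary reading is right, these comparisons would have wider intervals than the same data allow. The vaccination outcomes have no baseline value and are not affected.

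**Working it through.** **Inputs from the documents.** Allocation is 1:1:1, stratified on hesitant or non-hesitant status (Randomization). There are three follow-up surveys, but not every measure is in each:
- Attitudes are reassessed at 4-6 and 10-12 months. The 13-15 month section lists only hesitancy and satisfaction.
- The full five-item hesitancy score is available at 10-12 and 13-15 months, because only part of it is asked at 4-6 months.
- Intention is described as asked at every time point (All arms).

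**Inputs assumed.** The plan gives no SD, correlation, effect size, sample size or power for survey outcomes, so it has no figure to reproduce. I take SD 1 at every survey, a common correlation ρ between surveys, complete data among responders, and two-sided 5% tests.

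**Formulas.** For the mean of k follow-ups, the per-person variance entering the arm contrast is:
- difference-in-difference: (1 + (k−1)ρ)/k + 1 − 2ρ
- baseline-adjusted: (1 + (k−1)ρ)/k − ρ²

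The gap is 1 − 2ρ + ρ² = (1 − ρ)², which is positive for any ρ below 1. For k = 1 the variances are 2(1 − ρ) and 1 − ρ², so adjustment cuts the variance by (1 − ρ)/2.

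| ρ | k=1: change, adjusted | cut | k=2: change, adjusted | cut |
|---|---|---|---|---|
| 0.3 | 1.40, 0.91 | 35% | 1.05, 0.56 | 47% |
| 0.5 | 1.00, 0.75 | 25% | 0.75, 0.50 | 33% |
| 0.7 | 0.60, 0.51 | 15% | 0.45, 0.36 | 20% |
| 0.8 | 0.40, 0.36 | 10% | 0.30, 0.26 | 13% |

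**Power, illustrative.** Assume a 0.2 SD effect and 200 responders per arm. Power is Φ(0.2/√(2V/200) − 1.96), with V from the table.
- One survey, ρ = 0.5: 0.2/0.100 = 2.00 gives 52%; 0.2/0.0866 = 2.31 gives 64%.
- One survey, ρ = 0.7: 0.2/0.0775 = 2.58 gives 73%; 0.2/0.0714 = 2.80 gives 80%.
- Two surveys averaged, ρ = 0.5: 2.31 gives 64%; 2.83 gives 81%.
- Two surveys averaged, ρ = 0.7: 2.98 gives 85%; 3.33 gives 92%.

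**Do the listed covariates recover the loss?** In one simulated two-visit data set (150 per arm, correlation about 0.6), the mixed-model arm-by-time contrast equalled the raw difference in change scores: estimate −0.1816, SE 0.0982. Adding age, or age and a baseline stratum, as main effects left both unchanged to four decimals. A main effect that is constant over time cancels in a within-person change. A common baseline mean gave SE 0.0899, and regression on baseline gave SE 0.0893.

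**Does stratified randomization recover it?** I refer to 4,000 simulated trials per setting with two arms of about 150, a 0.25 SD effect, one follow-up, and permuted blocks within a stratum cut from the baseline score itself (15% hesitant, assumed). The empirical SD of the contrast, change against adjusted, was 0.1082 against 0.0998 at ρ = 0.5 and 0.0845 against 0.0802 at ρ = 0.7. The variance cuts are therefore 1 − (0.0998/0.1082)² = 15% and 1 − (0.0802/0.0845)² = 10%, smaller than the 25% and 15% without stratification. The SE that the change analysis reports does not reflect this: at ρ = 0.5 it averaged 0.1154 against a true 0.1082. Power therefore stayed lower for change: 59% against 70% at ρ = 0.5, 81% against 86% at 0.7, and 94% against 95% at 0.8.

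**The case against.** The strongest reply is that the lack of baseline adjustment is inferred from silence. The covariate list is open, no model is written out, and a mixed model with a common baseline mean also yields a difference-in-difference. This stands. A reader might infer that the plan rules out baseline adjustment, and the documents do not support that. What can be said is that the plan does not state how baseline enters, and that its wording points to the less efficient choice.

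Second, a reader might take the gain for the average of three follow-ups (37.5% at ρ = 0.5) as the size for all survey outcomes. The survey schedule does not support that. Attitudes, and the full hesitancy score, have two follow-ups. Contrasts at a single survey, which an arm-by-survey model naturally gives, gain less.

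Third, stratification on hesitancy already limits chance imbalance on that score. This stands in part: the true gain for hesitancy is likely to be smaller, but the planned model does not use the stratum in a way that shortens its intervals.

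Fourth, a reader might infer bias from the missing adjustment. Randomization keeps the expected baseline means equal, so with complete data the change contrast remains unbiased.

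Fifth, the plan wants to describe change over time, which a model of follow-up scores alone does not directly estimate for each arm. This is a fair but small cost. The partial hesitancy scale at 4-6 months is only a weak further argument for adjustment, since change could be computed on the items common to both surveys.

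**Conclusion.** The point holds as a loss of precision on the survey outcomes, conditional on the ordinary reading of difference-in-difference with a free baseline mean per arm. Under equal variances, adjustment would cut the contrast variance at one survey by 35% to 10%, and for two averaged surveys by 47% to 13%, as ρ runs from 0.3 to 0.8. At one survey, unadjusted intervals would be about 15% wider at ρ = 0.5 (√(1/0.75) = 1.15) and 8% wider at ρ = 0.7 (√(1/0.85) = 1.08).

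These sizes rest on assumed correlations, equal variances and complete data among responders. The power figures also rest on an assumed effect and sample size. The gain is small if scores are very stable (5% at one survey for ρ = 0.9) and may be smaller for hesitancy. It is still worth acting on, because the baseline scores are expected to be available for every participant.

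**What to change.** In the Analysis section, state how baseline enters the model. Base the arm comparisons on a mixed model of the follow-up scores with arm, survey, arm-by-survey, the baseline score of the same measure, baseline-by-survey, and the hesitancy stratum. The baseline-by-survey term lets the baseline slope differ between surveys.

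As an alternative, where the same scale is used at every survey, keep baseline as a repeated measure and constrain the arms to a common baseline mean. The two forms are close but not identical, and the second does not suit the shortened hesitancy measure at 4-6 months. State also whether the main contrast is at a single survey or an average over surveys.

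The cost is a change of wording, with no new data. The first form does not directly estimate each arm's own change, so keep change by arm as a descriptive summary.
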